6. CONFIDENTIALITY AND DATA STORAGE

We will use the IRB recommended RedCap for data storage (openREDCap.nyumc.org). We will also work with MCIT to set up a NYU shared network drive which is HIPAA compliant (for offsite backup storage) specifically for our study. All study personnel have already taken the mandatory HIPAA and Patient Privacy/Confidentiality training modules required by our institutional IRBs, to ensure that they are aware of the importance of patient confidentiality and all appropriate laws regarding protection against privacy breaches. Procedures will be in place to ensure that all files containing subject information will be kept in locked filing cabinets or password-protected electronic databases on a secure server. The majority of study data and all interview transcripts will be maintained in electronic files with no patient identifiers other than a study ID number; there will be one file maintained separately with its own password protection that links study ID numbers to patient identifying information.

No identifiable information about study participants will be disclosed to individuals outside those approved by the IRB to be on the study protocol. No publications that result from the study will identify individual participants.

Transcript files will also be password-protected and user-restricted. We will delete potential identifiable information from transcripts and audio recordings one year after the study ends. We will also encourage participants to use pseudonyms during focus groups and/or interviews. During each focus group or interview session, the study PI will emphasize the importance of privacy and confidentiality of the discussion within the group. The text-message-based video counseling will be protected via password-enabled access. Only study participants will have access codes to open these videos. Others in the same household would not be able to open the video, unless participants choose to share the access code.

7. DATA ANALYSIS AND DATA MONITORING

7.1 Data Analysis

K99-phase Aim 1: All focus groups will be audio-recorded and transcribed verbatim into Microsoft Word. Atlas will be used to store, organize, retrieve, and analyze the qualitative data. Thematic analysis will be used to analyze qualitative data.⁶¹ To establish coding reliability, the RA and PI will independently code up to 10% of the transcripts and identify kappa coefficient.⁶² We will meet weekly to review definitions and assignment of codes, and resolve differences through consensus. If no agreement can be made, the study team will be consulted. The RA and PI will read all transcripts and develop an open coding schema based on emergent theses. We will present coding schemes to study team, discuss emergent themes, refine codes, and develop a codebook that consists of a list of categories and topics. Once all data have been coded based on the codebook, codes most relevant to the research questions will be subject to further analysis. For the quantitative data, a paired t-test will be used to determine pre-post change in HbA1c. Descriptive statistics will be used to summarize participants' satisfaction with the SMS intervention.

R00-phase Aim 2: We will employ the "intent to treat" (ITT) approach in analyses. We will perform a detailed descriptive analysis of all the data collected in the study. These preliminary descriptive statistics will be used to 1) check accuracy and completeness of inputted data, 2) describe univariate distribution of each variable at baseline, and 3) examine the associations between variables. We will also explore features of the data (e.g., amount and pattern of missing data, outliers, excess zeros, departures from distributional assumptions) to determine whether special techniques are needed.

Aim 2a: Establish the proof of concept regarding the efficacy of the SMS intervention for glycemic control in Chinese Americans with T2D. We will test whether the 2 groups are comparable on baseline sociodemographic, health characteristics, and levels of acculturation. If significant differences are found, we will include the variables as covariates in the models. Between group and group by time interaction effects will be examined graphically and via linear mixed modeling for HbA1c. Calculated effect sizes will be used for sample size estimation needed for a two-sided alpha of 0.05 and power of 0.80 for the larger scale R01 study.

Exploratory Aim 2b: Explore the potential effects of the SMS intervention on psychosocial and behavioral factors in glycemic control. For continuous secondary outcome variables (self-efficacy, adherence, and dietary data), linear mixed modeling will be used to examine the group and group by time interaction effects for each outcome at 3- and 6-months. For the physical activity data, we will use a GEE logistic model to examine whether there are group differences in the proportions of participants achieving 150 minutes/week of physical activity at any level of intensity and at a moderate- or greater intensity level.

Rutgers Mental Health Pilot

Aim 2c: Examine current mental health burden and psychosocial support and how they are related to diabetes self-care behaviors and glycemic control in Chinese Americans with

T2D. We will use descriptive statistics to summarize mental health burden and psychosocial support in Chinese immigrants with T2D. We will describe the percent of the sample who has elevated stress, anxiety and depressive symptoms and the current social support and coping strategies. We will also use correlation to examine the relationships between the mental health burden and diabetes self-management behaviors and HbA1c (measured in R00 study).

Aim 2d: Characterize barriers to accessing mental health services and understand needs and preferences in Chinese Americans with T2D. Similar to the analytic approach used in the K99 Aim 1 analyses, all focus groups will be audio-recorded and transcribed verbatim into Microsoft Word. Atlas will be used to store, organize, retrieve, and analyze the qualitative data. Thematic analysis will be used to analyze qualitative data.⁵⁹

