3.3. Characteristics of the Research Population

Phase 1: K99 Phase Feasibility Study Inclusion criteria: To be eligible for the study, participants must: 1) self-identify as Chinese Immigrant or Chinese American; 2) be 18-75 years old, 3) be able to speak and understand Mandarin; 4) self-report a diagnosis of T2D; 5) know how to do a finger stick blood sugar test; 6) be willing to do a finger stick blood glucose test for each study visit; 7) baseline HbA1c $\geq 7\%$; 8) be currently using WeChat; 9) be willing to receive WeChat messages regarding T2D management, 9 10) express strong interest and confidence in finishing watching 2 diabetes videos each week for a total of 12 weeks; 11) be motivated to make lifestyle changes to control their diabetes.

Phase 1: K99 Phase Feasibility Study Exclusion criteria: Individuals will be excluded from participation if they meet any of the following:(1) unable or unwilling to provide informed consent; (2) unable to participate meaningfully in the intervention (e.g., uncorrected sight and hearing impairment); (3) unwilling to accept randomization assignment; (4) pregnant, plans to becomes pregnant in the next 6 months, or who become pregnant during the study, or (5) breastfeeding or

(6) live in a facility or other health care setting where they have no control over diabetes self-management.

Phase 2 R00 Phase pilot RCT Inclusion criteria: To be eligible for the study, participants must: 1) self-identify as Chinese Immigrant or Chinese American; 2) be 18-70 years old, 3) be able to speak and understand Mandarin; 4) self-report a diagnosis of T2D; 5) baseline HbA1c $\geq 7\%$; 6) be currently using WeChat or text messages; 7) be willing to receive WeChat or text messages regarding T2D management, 8) express strong interest and confidence in finishing watching 2 diabetes videos each week for a total of 12 weeks; 9) be motivated to make lifestyle changes to control their diabetes; 10) be willing to wear ActiGraph for 8 days.

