4.3.2 K99 Phase Pre-, Post-Test Evaluation Procedures

We will conduct a 3-month, single group, pre-, post-test study to assess the feasibility and acceptability of the SMS-based diabetes video counseling. We will recruit a randomly selected sample of approximately 30 Chinese Americans with T2D from the CBWCHC or private practices or community centers.

We will first conduct phone screening for the interested participants. After they pass the phone screening, we will schedule the first baseline visit. During the baseline visit, the study staff will first explain the study and consent form to the participants. After the consent form is signed, study staff will ask participants to perform a finger stick to check their HbA1c levels. If the A1c level is greater or equal to 7%, the study staff will continue with the study survey. Otherwise, study staff will thank participants for their interest and time and pay \$30 for their time.

For those who are eligible to continue to participant, they will be asked several survey questions and then subscribed to our diabetes videos. They will receive 1-2 SMS-based counseling videos every week for 12 weeks (each video is about 5-10 minutes in duration). HbA1c will be assessed at baseline and again at 3 and 6 months. At the end of the 3-month intervention, we will conduct focus groups with participants to assess the feasibility and acceptability of SMS-based video sessions, perceived usefulness of the video sessions, and recommendations for improvement. All of the focus group interviews will be recorded and transcribed. Acceptability will also be assessed by a satisfaction questionnaire used in a prior study. Changes and refinements will be made to the preliminary intervention content and delivery based on the feedback, which will be tested in the R00 study. We will also help participant to set goals for their diabetes management and then have biweekly phone call follow-ups to check in their progress toward the goal and

problem solve any raised questions/concerns.

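### The K99 paired t-test takes as its pre-value the same finger-stick HbA1c that had to be at least 7% for entry, so regression to the mean alone can produce a significant fall.

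*Combined protocol and SAP*

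**What the plan says.** Section 4.3.2 describes the K99 evaluation as a "3-month, single group, pre-, post-test study to assess the feasibility and acceptability" of the videos, in "approximately 30 Chinese Americans with T2D". At the baseline visit, after consent, "study staff will ask participants to perform a finger stick to check their HbA1c levels". The next step is a gate: "If the A1c level is greater or equal to 7%, the study staff will continue with the study survey". Anyone below 7% is thanked, paid and not continued. Section 3.3 lists the same threshold as an inclusion criterion and calls the reading the baseline HbA1c.

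On follow-up, Section 4.3.2 says "HbA1c will be assessed at baseline and again at 3 and 6 months". No second baseline reading is described.

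The only HbA1c analysis for this study is in Section 7.1 under K99-phase Aim 1: "a paired t-test will be used to determine pre-post change in HbA1c". That section does not say whether the post value is the 3-month or the 6-month one, gives no alpha for this test, and does not mention regression to the mean.

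**The concern.** A paired t-test against zero takes zero as the mean change to expect if the intervention does nothing. That fails when people are kept only because their first reading reached a cut-off. Some of those at or above 7% on the day are there partly through short-term variation or measurement error, and their next reading will on average be lower. People whose variation went the other way were turned away, so nothing offsets the fall. With no control group, the analysis cannot separate this fall from an effect of the videos.

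At stake is the reading of the one inferential HbA1c result that the K99 study would yield. HbA1c is also the R00 primary outcome, and a significant uncontrolled fall could be quoted as early benefit. The plan contains no sentence that limits this.

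**Working it through.** The plan gives no effect size, power or error rate for this test, so there is no figure of its own to reproduce.

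**Inputs from the documents:** cut-off 7%; about 30 participants; one group; one baseline reading, which is also the gate (Sections 3.3 and 4.3.2); paired t-test (Section 7.1).

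**Assumptions, not in the documents:** HbA1c among those tested is normal with mean m of 7.0-8.0% and SD of 1.0-1.5; correlation r of baseline with follow-up is 0.6-0.9; mean and SD are stable over time; no true effect. I take a two-sided alpha of 0.05. The plan names this level only for a later trial ("two-sided alpha of 0.05 and power of 0.80 for the larger scale R01 study"). The nominal chance of a significant fall is half of 5%, which is 2.5%.

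**Step 1, expected fall with no effect.** With a = (7 - m)/SD,

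expected fall = (1 - r) × SD × φ(a) / [1 - Φ(a)].

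- Smallest in the range (m 8.0, SD 1.0, r 0.9): a = -1; φ/(1 - Φ) = 0.242/0.841 = 0.288; fall = 0.1 × 1.0 × 0.288 = 0.03.
- Middle (m 7.5, SD 1.2, r 0.8): a = -0.417; 0.366/0.662 = 0.553; fall = 0.2 × 1.2 × 0.553 = 0.13.
- Largest (m 7.0, SD 1.5, r 0.6): a = 0; 0.399/0.500 = 0.798; fall = 0.4 × 1.5 × 0.798 = 0.48.

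**Step 2, chance of a significant fall.** Simulation of 20,000 trials per scenario, n = 30, no true effect:

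| Mean | SD | r | Expected fall | Chance of a significant fall |
|---|---|---|---|---|
| 7.5, no gate | 1.2 | 0.8 | 0.00 | 2.6% |
| 8.0 | 1.0 | 0.9 | 0.03 | 5% |
| 8.0 | 1.0 | 0.8 | 0.06 | 7% |
| 7.5 | 1.2 | 0.9 | 0.07 | 10% |
| 7.5 | 1.2 | 0.8 | 0.13 | 16% |
| 7.5 | 1.2 | 0.6 | 0.27 | 28% |
| 7.0 | 1.0 | 0.8 | 0.16 | 28% |
| 7.0 | 1.0 | 0.6 | 0.32 | 52% |
| 7.0 | 1.5 | 0.6 | 0.48 | 53% |

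Without the gate the test behaves as it should, so the excess comes from the gate. With 24 completers in the middle scenario the chance is 13% instead of 16%. On a wider grid (mean 6.5-8.5, r 0.5-0.95) the fall runs from 0.01 to 0.77 points and the chance from 3% to 92%. The direction is firm, but the size depends heavily on the assumptions.

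**Step 3, can it be corrected from the study's own data?** The finger-stick is taken before anyone is turned away, so the mean of all readings estimates m. Selection on baseline does not bias the slope b of follow-up on baseline among those enrolled, provided the relation is linear. Then

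corrected change = observed mean change + (1 - b) × (baseline mean of enrolled - mean of all finger-sticks).

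In the middle scenario the enrolled baseline mean is 7.5 + 1.2 × 0.553 = 8.16. The added term is 0.2 × 0.66 = 0.13, which cancels the expected fall of 0.13. In simulation with no effect this estimator averaged within 0.01 points of zero.

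**The case against.** The strongest reply is that nothing in the plan turns on this test. Section 2.2 gives Aim 1c as feasibility and acceptability. Section 4.3.2 bases refinement of the intervention on participants' feedback. Efficacy belongs to Aim 2a in the randomized R00 phase, where both arms meet the same 7% criterion, so regression to the mean does not by itself create a group difference. Section 7.1 takes the effect sizes for the R01 from Aim 2a. A reader might infer that a spurious K99 fall could decide whether R00 goes ahead or distort the R01 sample size. The documents do not support that, and this part of the reply stands in full.

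A second reply concerns size. The calculation treats those tested as unselected, yet Section 4.3.2 has a phone screen first and Section 4.1 has providers referring potentially eligible patients. Whether an earlier HbA1c was used for K99 is not stated. If a prior reading also had to reach 7%, with all correlations 0.8, the middle scenario drops to a fall of 0.09 and a chance of 9%. The artefact shrinks but stays above 2.5%.

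Third, the plan never says outright that the gating finger-stick is the pre-value. That is so, but it describes no other K99 baseline HbA1c.

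Fourth, a correction needs quantities that the documents lack. The study could supply them from its own finger-sticks, but the documents do not say whether readings below 7% were kept.

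**Conclusion.** The concern holds as a matter of analysis and reporting. Followed as written, the paired t-test exceeds its nominal 2.5% chance of a significant fall. Under the stated assumptions the chance is about 5-53% and the artefactual fall about 0.03-0.48 points. It lies near the low end if most people tested are well above 7% and readings correlate highly, and lower still if they had already been screened on HbA1c.

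A reader might go further and infer that a fall is guaranteed, or that a significant result would be spurious. Neither follows. The expected fall requires a stable mean and comparable measurement at both times. Section 4.3.2 moves the follow-up surveys to the phone without saying how HbA1c is then obtained. Significance by artefact is possible, and in much of the range it is the less likely outcome.

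The consequence is limited to the interpretation of the K99 HbA1c change. The R00 comparison and the R01 sizing are not affected.

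**What to change.** Section 3.1 says all K99 participants had finished by 9/28/2022, so a second, non-gating baseline reading can no longer be added. The analysis and its wording can still change:

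- Drop the paired t-test as an inferential test. Report the mean change with its 95% CI, labelled uncontrolled and descriptive. The interval alone is not enough, because it carries the same bias as the test.
- Beside it, report the corrected change from Step 3, using the mean of all baseline-visit finger-sticks, including those below 7%, and the slope among those enrolled. Give their SD as well, so that the truncated-normal figure can be checked. Add a sensitivity range for the correlation, for example 0.6-0.9. This matters because an intervention effect that varies with baseline would also alter the slope.
- If readings below 7% were not kept, show the truncated-normal expectation over a stated range of mean, SD and correlation instead.
- Do not use the last medical-record HbA1c as the pre-value. Record abstraction is described for R00, not K99, and such a value may itself have influenced referral.
- State whether post means 3 or 6 months, and that the K99 change is neither evidence of efficacy nor an effect size.

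The cost is a few sentences and a short calculation. The corrected estimate is less precise than the raw change, and the reported change will be less favourable.

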3. METHODS AND PROCEDURES

3.1 Study Design

K99 Phase

Qualitative focus groups/interviews (N=20): We will conduct focus groups/interviews to understand barriers and facilitators of glycemic control in Chinese Americans with T2D and to develop culturally and linguistically tailored SMS intervention content.

Quantitative pre-, post-test evaluation (N=30): We will assess the feasibility and acceptability of the SMS intervention in a 3-month, single group pre-, post-test study among 30 Chinese Americans with T2D.

R00 Phase

Pilot RCT (N=60): Participants will be randomized to one of 2 arms (n=30 each): 1) wait-list control; or 2) SMS intervention. We will evaluate changes in HbA1c at baseline, 3-, and 6-months. In exploratory analyses, we will test mediators (e.g., self-efficacy, diabetes self-management behaviors, diet intake, and physical activity).

Rutgers Mental Health Pilot

Cross-sectional quantitative survey (N=133): We will contact the participants from K99, R00 phase (s18-00609), and FAMILY study (s19-01275) to ask whether they are interested in joining this mental health pilot and answering a few additional questions. Our target goal is 133. As of 9/28/2022, all participants from K99, R00 and FAMILY completed their assessments, intervention and participation with us. We will administer this mental health survey once this pilot modification was approved by the IRB. This will be a one-time survey administration because the goal of the pilot was to get a snapshot of the mental health burden in Chinese Americans with T2D. We are

not examining changes over time in mental health, thus, we will not repeat the survey at 3 or 6 months.

Qualitative focus groups (N=10-16): Guided by the NIMHD Research Framework,⁴¹ we will assess facilitators and barriers to accessing mental health services in Chinese Americans with T2D. We will explore factors on multiple levels, including individual, interpersonal, community, health system, and societal levels. We will select 10-15 participants based on their survey responses (who reported elevated stress, anxiety, or depressive symptoms) to join the focus groups (2 focus groups; 5-8 participants per group) to gain a deeper understanding of barriers to utilizing mental health services. We will also ask participants' preferences for mental health support (e.g., individual vs. group-based, in-person vs. phone vs. video-based).

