2. **Diabetes Self-Management Behaviors:** We will administer the adapted Summary of Diabetes Self-Care Activities (SDSCA) measure⁴³ to assess participants' adherence to diabetes self-management behaviors. This scale consists of 13 items and asks participants to describe their diabetes self-care activities over the past 7 days.
3. **Dietary Intake:** Informed by a previous study in Chinese Americans,⁴⁴ we will use the adapted Mediterranean Dietary Screener⁴⁵ to estimate dietary intake behaviors in our participants at baseline, 3- and 6-months.
4. **Physical Activity:** We will use the International Physical Activity Questionnaire (IPAQ)^{46,47} short version to assess the frequency and duration of various physical activities undertaken by adults over the past 7 days. This scale will provide an estimate of the number of minutes per week participants engage in each category of physical activity (e.g., vigorous, moderate, and mild intensity). We will also use the ActiGraph to objectively measure physical activity and sleep. Our study staff will distribute and collect the device to participants once they are eligible for the study. Once we receive the device, we will download the data.

Covariates: Sociodemographic, health characteristics, and acculturation. We will use a sociodemographic questionnaire to collect basic information about the participant such as age, gender, education, income, duration of residence in the US, health insurance, the diabetes medication regimen, duration of T2D, and medical history. Informed by prior literature, we will also include surveys to measure Health Beliefs, Diabetes Knowledge, Diabetes Distress, Social Support, Mental Health, the Impact of COVID-19, and memory test, which also play essential roles in diabetes management.

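### HbA1c covariates are chosen by baseline significance tests, and the role of baseline HbA1c in the mixed model is not stated: a cheap improvement of modest size

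*Combined protocol and SAP*

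**What the plan says.** The document is the combined protocol and SAP. For Aim 2a, Section 7.1 begins with baseline testing: "We will test whether the 2 groups are comparable on baseline sociodemographic, health characteristics, and levels of acculturation." The next sentence makes adjustment depend on the result: "If significant differences are found, we will include the variables as covariates in the models." It gives no significance level for these tests and names no covariate that is always included.

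The model is described in one sentence: "Between group and group by time interaction effects will be examined graphically and via linear mixed modeling for HbA1c." On its use, the section says: "Calculated effect sizes will be used for sample size estimation", meaning the later R01 trial.

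Section 3.1 gives the HbA1c time points: "We will evaluate changes in HbA1c at baseline, 3-, and 6-months." In Section 4.3.3 the covariates paragraph lists "age, gender, education, income, duration of residence in the US, health insurance, the diabetes medication regimen, duration of T2D, and medical history", under an opening that also names acculturation, and then adds surveys of "Health Beliefs, Diabetes Knowledge, Diabetes Distress, Social Support, Mental Health, the Impact of COVID-19, and memory test". Baseline HbA1c is not in that list. It is, however, an R00 entry criterion in Section 3.3 ("4) self-report a diagnosis of T2D; 5) baseline HbA1c", with a minimum of 7%), so a value should exist for every participant.

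No section available to us says whether baseline HbA1c is a repeated response, a covariate, part of a change score, or constrained to be equal between arms.

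**The concern.** There are two separate gaps, and closing one does not close the other.

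The first is the selection rule. Allocation is by a computer-generated scheme, so any baseline difference between arms is due to chance. A test of that difference says nothing about whether the variable predicts HbA1c, which is the usual reason to adjust. The adjustment set is also unknown until the tests have been seen.

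The second is baseline HbA1c itself, usually the strongest available predictor of later HbA1c. If it counts as a health characteristic under the rule, it is adjusted for only when the arms happen to differ. If all three visits are modelled as responses, the group-by-time contrast is a difference in change from baseline, which has a larger variance than a baseline-adjusted difference.

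At stake are the precision and reproducibility of the effect size carried to the R01.

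**Working it through.** The plan states no effect size, SD, power or correlation for the pilot, so there is no figure to reproduce. From the documents: 30 per arm, visits at baseline, 3 and 6 months, entry floor of HbA1c 7%. Assumed: 0.05 level for the baseline tests, correlation rho between visits of 0.5-0.7, and a treatment effect of 0.6 SD, the SD being that of HbA1c before the floor is applied.

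**1. How often the rule acts.**
- A continuous variable enters if the arms differ by more than t(0.975, 58) × √(2/30) = 0.517 SD. By construction that happens in 5% of trials, whatever its prognostic value.
- Candidates: nine listed items plus acculturation, so 10. Chance that at least one enters: 1 − 0.95^10 = 0.40 if independent; 0.32 in simulation if mutually correlated 0.4.

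**2. What the rule does to the estimates.**
- Group-by-time (random-intercept model, covariate correlated 0.4 with HbA1c): adding a time-constant covariate changed the 6-month estimate by less than 1e-14 with complete data. With 20% missing follow-up the SE ratio was 0.998.
- Between-group term averaged over three visits, rho 0.6. Without adjustment the variance is (1 + 2 × 0.6)/3 × 2/30 = 0.0489, so the SD is 0.221 (0.220 simulated). For a covariate correlated 0.3 with HbA1c, simulated SDs are 0.217 under the rule and 0.208 with fixed adjustment.
- When that covariate enters, the estimate moves by about 0.18 SD on average, and its root mean squared error falls from 0.274 to 0.213. The movement is a correction.
- Type I error under the rule, single follow-up: 3.4-4.7% in the simulations run.

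**3. Baseline HbA1c.** Take a normal source population with unit variance at each visit. Truncating baseline at 7% reduces its variance to k but leaves the regression slope (rho) and the residual variance (1 − rho²) unchanged. At one follow-up visit:
- variance of change = (1 − rho²) + k(1 − rho)²
- baseline-adjusted variance = 1 − rho²
- ratio, adjusted to change = (1 + rho)/[(1 + rho) + k(1 − rho)]

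If 30%, 50% or 70% of the source population lies below 7%, k = 0.493, 0.363 or 0.265. Power below is from the noncentral t with noncentrality 0.6/√(V × 2/30), where V is the relevant variance.

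| rho | k | V change | V adjusted | ratio | power, change | power, adjusted |
|---|---|---|---|---|---|---|
| 0.5 | 0.493 | 0.873 | 0.750 | 0.86 | 68.6% | 75.1% |
| 0.6 | 0.493 | 0.719 | 0.640 | 0.89 | 76.9% | 81.5% |
| 0.6 | 0.265 | 0.682 | 0.640 | 0.94 | 79.0% | 81.5% |
| 0.7 | 0.265 | 0.534 | 0.510 | 0.96 | 87.8% | 89.2% |

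So 4-14% of variance is removed, worth about 1.4 to 6.5 power points. Allowing for the small cost of estimating the covariate effect lowers the adjusted power at rho 0.6 from 81.5% to 80.8%.

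**4. Which contrast.** With baseline as a response and a constant effect d at 3 and 6 months, a group term averaged over the three visits estimates (0 + d + d)/3 = 2d/3. For d = 0.6 SD that is 0.4 SD.

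**The case against.** The strongest reply is that the rule has almost no consequence. That largely stands: group-by-time is unaffected, type I error is not inflated, and the rule is slightly better than making no adjustment. The pilot has no power target, and treating baseline as a response is a legitimate longitudinal model. What remains is that the rule is less precise than fixed adjustment, and that the model and contrast behind the R01 effect size are not defined.

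Four stronger readings are tempting, and the documents do not support them.

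- A reader might infer that chance entry of a covariate contaminates the effect size. When a covariate enters, the shift corrects a chance imbalance and reduces error.
- A reader might count all 17 variables in Section 4.3.3, giving 1 − 0.95^17 = 58%. Section 7.1 tests only sociodemographic variables, health characteristics and acculturation, and most of the seven further survey domains do not clearly belong there. Ten is the closer count.
- A reader might quote the gain without an entry floor: ratio (1 + rho)/2, so 25% of variance at rho 0.5, and 72% v 81% power at rho 0.6. Section 3.3 sets a floor, which shrinks the gain.
- A reader might compare baseline-adjusted analysis with one that ignores baseline altogether (63% v 81% at rho 0.6). Only the Aim 2b text on secondary outcomes is worded that way.

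The difference-in-change reading is itself an inference from Sections 3.1 and 7.1, because the plan does not state the model.

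**Conclusion.** The point holds as a cheap improvement of modest size. Covariates for the HbA1c model are selected by tests that cannot identify prognostic variables, and the role of baseline HbA1c is unstated. The rule itself costs little: SD 0.217 against 0.208 on the between-group term for one covariate correlated 0.3. The main gain is from always adjusting for baseline HbA1c: about 4-14% of variance, or roughly 1-6.5 power points, if the plan's contrast is a difference in change. That range rests on assumed correlations of 0.5-0.7, a 0.6 SD effect, a normal source population and no missing data. No figure in the plan is wrong, and nothing here shows the planned analysis to be biased or invalid.

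**What to change.** 1. Delete the baseline significance tests and the conditional rule. Present baseline characteristics descriptively.
2. Always include baseline HbA1c, in one of two stated ways (not both):
   - as a covariate, with the 3- and 6-month values as outcomes and group, visit and group-by-visit terms; or
   - as a response with a common baseline mean in both arms and an unstructured covariance. The covariance matters: because of the entry floor, baseline variance is smaller than follow-up variance, and a random-intercept version had 7.3-8.4% type I error in simulation at rho 0.6.
3. Name the contrast that feeds the R01 effect size, since a group term averaged over three visits including baseline keeps only two-thirds of a constant post-baseline effect.
4. Further covariates are optional. If used, fix a short list regardless of imbalance.

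Cost: a text change, no new data, and 1 degree of freedom for baseline as a covariate. That version also omits randomised participants with no follow-up HbA1c, which bears on the intent-to-treat statement in Section 7.1. Such gaps are plausible, because Section 4.3.3 takes HbA1c from usual-care tests done every 3-6 months. The common-baseline version keeps those participants in the model.

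Timing: Section 3.1 says R00 participation was complete by 28 September 2022. The choice counts as prespecified only if it is dated before any comparison of HbA1c by arm; otherwise label the adjusted model post hoc.
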